7.2.3 Events of Clinical Interest

Selected non-serious and serious adverse events are also known as Events of Clinical Interest (ECI) and must be reported within 24 hours to the Sponsor and within 2 working days to Merck Global Safety. (Attn: Worldwide Product Safety; [contact]).

For the time period beginning when the consent form is signed until treatment allocation/randomization, any ECI, or follow up to an ECI, that occurs to any subject must be reported within 24 hours to the Sponsor and within 2 working days to Merck Global Safety if it causes the subject to be excluded from the trial, or is the result of a protocol-specified intervention, including but not limited to washout or discontinuation of usual therapy, diet, placebo treatment or a procedure.

For the time period beginning at treatment allocation/randomization through 90 days following cessation of treatment, or 30 days following cessation of treatment if the subject initiates new anticancer therapy, whichever is earlier, any ECI, or follow up to an ECI, whether or not related to Merck product, must be reported within 24 hours to the Sponsor and within 24 hours to Merck Global Safety.

Events of clinical interest for this trial include:

1. an overdose of Merck product, as defined in Section 7.2. - Definition of an Overdose for This Protocol and Reporting of Overdose to the Sponsor, that is not associated with clinical symptoms or abnormal laboratory results.
2. an elevated AST or ALT lab value that is greater than or equal to 3X the upper limit of normal and an elevated total bilirubin lab value that is greater than or equal to 2X the upper

Product: Pembrolizumab

Protocol/Amendment No.: May 18, 2020v2.0

limit of normal and, at the same time, an alkaline phosphatase lab value that is less than 2X the upper limit of normal, as determined by way of protocol-specified laboratory testing or unscheduled laboratory testing.*

***Note:** These criteria are based upon available regulatory guidance documents. The purpose of the criteria is to specify a threshold of abnormal hepatic tests that may require an additional evaluation for an underlying etiology.

7.2.4 Protocol-Specific Exceptions to Serious Adverse Event Reporting

Efficacy endpoints as outlined in this section will not be reported to Merck as described in Section 7.2.3 - Immediate Reporting of Adverse Events to the Sponsor and to Merck, unless there is evidence suggesting a causal relationship between the drug and the event. Any such event will be submitted to the Sponsor within 24 hours and to Merck Global Safety within 2 working days either by electronic or paper media.

Specifically, the suspected/actual events covered in this exception include any event that is disease progression of the cancer under study.

The Sponsor will monitor unblinded aggregated efficacy endpoint events and safety data to ensure the safety of the subjects in the trial. Any suspected endpoint which upon review is not progression of the cancer under study will be forwarded to Merck Global Safety as a SAE within 2 working days of determination that the event is not progression of the cancer under study

Hospitalization related to convenience (e.g. transportation issues etc.) will not be considered a SAE.

7.2.5 Evaluating Adverse Events

An investigator who is a qualified physician will evaluate all adverse events according to the NCI Common Terminology for Adverse Events (CTCAE), version 4.03. Any adverse event which changes CTCAE grade over the course of a given episode will have each change of grade recorded on the adverse event case report forms/worksheets.

All adverse events regardless of CTCAE grade must also be evaluated for seriousness.

Table 13: Evaluating Adverse Events

An investigator who is a qualified physician, will evaluate all adverse events as to:

V4.0 CTCAE Grading	Grade 1	Mild; asymptomatic or mild symptoms; clinical or diagnostic observations only; intervention not indicated.
	Grade 2	Moderate; minimal, local or noninvasive intervention indicated; limiting age-appropriate instrumental ADL.
	Grade 3	Severe or medically significant but not immediately life-threatening; hospitalization or prolongation of hospitalization indicated; disabling; limiting self-care ADL.
	Grade 4	Life threatening consequences; urgent intervention indicated.
	Grade 5	Death related to AE
Seriousness	A serious adverse event is any adverse event occurring at any dose or during any use of Merck product that:	
	† Results in death; or	
	† Is life threatening; or places the subject, in the view of the investigator, at immediate risk of death from the event as it occurred (Note: This does not include an adverse event that, had it occurred in a more severe form, might have caused death.); or	
	† Results in a persistent or significant disability/incapacity (substantial disruption of one's ability to conduct normal life functions); or	
	† Results in or prolongs an existing inpatient hospitalization (hospitalization is defined as an inpatient admission, regardless of length of stay, even if the hospitalization is a precautionary measure for continued observation. (Note: Hospitalization for an elective procedure to treat a pre-existing condition that has not worsened is not a serious adverse event. A pre-existing condition is a clinical condition that is diagnosed prior to the use of a Merck product and is documented in the patient's medical history.); or	
	† Is a congenital anomaly/birth defect (in offspring of subject taking the product regardless of time to diagnosis); or	
	Is a new cancer (that is not a condition of the study) (although not serious per ICH definition, is reportable to the Sponsor within 24 hours and to Merck within 2 working days to meet certain local requirements); or	
	Is an overdose (whether accidental or intentional). Any adverse event associated with an overdose is considered a serious adverse event for collection purposes. An overdose that is not associated with an adverse event is considered a non-serious event of clinical interest and must be reported within 24 hours to the Sponsor and to Merck within 2 working days..	

	Other important medical events that may not result in death, not be life threatening, or not require hospitalization may be considered a serious adverse event when, based upon appropriate medical judgment, the event may jeopardize the subject and may require medical or surgical intervention to prevent one of the outcomes listed previously (designated above by a †).						
Duration	Record the start and stop dates of the adverse event. If less than 1 day, indicate the appropriate length of time and units						
Action taken	Did the adverse event cause Merck product to be discontinued?						
Relationship to Merck Product	
Did Merck product cause the adverse event? The determination of the likelihood that Merck product caused the adverse event will be provided by an investigator who is a qualified physician. The investigator's signed/dated initials on the source document or worksheet that supports the causality noted on the AE form, ensures that a medically qualified assessment of causality was done. This initialed document must be retained for the required regulatory time frame. The criteria below are intended as reference guidelines to assist the investigator in assessing the likelihood of a relationship between the test drug and the adverse event based upon the available information.
 
The following components are to be used to assess the relationship between Merck product and the AE; the greater the correlation with the components and their respective elements (in number and/or intensity), the more likely Merck product caused the adverse event (AE):
 

Exposure	Is there evidence that the subject was actually exposed to Merck product such as: reliable history, acceptable compliance assessment (pill count, diary, etc.), expected pharmacologic effect, or measurement of drug/metabolite in bodily specimen?	

Time Course	Did the AE follow in a reasonable temporal sequence from administration of Merck product? Is the time of onset of the AE compatible with a drug-induced effect (applies to trials with investigational medicinal product)?	

Likely Cause	Is the AE not reasonably explained by another etiology such as underlying disease, other drug(s)/vaccine(s), or other host or environmental factors	

	Exposure	Is there evidence that the subject was actually exposed to Merck product such as: reliable history, acceptable compliance assessment (pill count, diary, etc.), expected pharmacologic effect, or measurement of drug/metabolite in bodily specimen?	Time Course	Did the AE follow in a reasonable temporal sequence from administration of Merck product? Is the time of onset of the AE compatible with a drug-induced effect (applies to trials with investigational medicinal product)?	Likely Cause	Is the AE not reasonably explained by another etiology such as underlying disease, other drug(s)/vaccine(s), or other host or environmental factors
Exposure	Is there evidence that the subject was actually exposed to Merck product such as: reliable history, acceptable compliance assessment (pill count, diary, etc.), expected pharmacologic effect, or measurement of drug/metabolite in bodily specimen?						
Time Course	Did the AE follow in a reasonable temporal sequence from administration of Merck product? Is the time of onset of the AE compatible with a drug-induced effect (applies to trials with investigational medicinal product)?						
Likely Cause	Is the AE not reasonably explained by another etiology such as underlying disease, other drug(s)/vaccine(s), or other host or environmental factors						

Product: Pembrolizumab/MK-3475**Protocol/Amendment No.: May 18, 2020v2.0**

Relationship to Merck Product (continued)	The following components are to be used to assess the relationship between the test drug and the AE: (continued)	
	Dechallenge	
Was Merck product discontinued or dose/exposure/frequency reduced?
 
If yes, did the AE resolve or improve?
 
If yes, this is a positive dechallenge. If no, this is a negative dechallenge.
 
(Note: This criterion is not applicable if: (1) the AE resulted in death or permanent disability; (2) the AE resolved/improved despite continuation of the Sponsor's product; or (3) the trial is a single-dose drug trial); or (4) Sponsor's product(s) is/are only used one time.)

	Rechallenge	
Was the subject re-exposed to Merck product in this study?
 
If yes, did the AE recur or worsen?
 
If yes, this is a positive rechallenge. If no, this is a negative rechallenge.
 
(Note: This criterion is not applicable if: (1) the initial AE resulted in death or permanent disability, or (2) the trial is a single-dose drug trial); or (3) Sponsor's product(s) is/are used only one time).
 
NOTE: IF A RECHALLENGE IS PLANNED FOR AN ADVERSE EVENT WHICH WAS SERIOUS AND WHICH MAY HAVE BEEN CAUSED BY MERCK PRODUCT, OR IF REEXPOSURE TO MERCK PRODUCT POSES ADDITIONAL POTENTIAL SIGNIFICANT RISK TO THE SUBJECT, THEN THE RECHALLENGE MUST BE APPROVED IN ADVANCE BY THE SPONSOR AS PER DOSE MODIFICATION GUIDELINES IN THE PROTOCOL.

	Consistency with Trial Treatment Profile	Is the clinical/pathological presentation of the AE consistent with previous knowledge regarding Merck product or drug class pharmacology or toxicology?
The assessment of relationship will be reported on the case report forms /worksheets by an investigator who is a qualified physician according to his/her best clinical judgment, including consideration of the above elements.		
Record one of the following		Use the following scale of criteria as guidance (not all criteria must be present to be indicative of Merck product relationship).
Yes, there is a reasonable possibility of Merck product relationship.		There is evidence of exposure to Merck product. The temporal sequence of the AE onset relative to the administration of Merck product is reasonable. The AE is more likely explained by Merck product than by another cause.
No, there is not a reasonable possibility of Merck product relationship		Subject did not receive the Merck product OR temporal sequence of the AE onset relative to administration of Merck product is not reasonable OR the AE is more likely explained by another cause than the Merck product. (Also entered for a subject with overdose without an associated AE.)

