5.3 Trial Treatments

The treatment to be used in this trial is outlined below in Table 6

Table 6: Trial Treatment

Drug	Dose/Potency	Dose Frequency	Route of Administration	Regimen/Treatment Period	Use
Lenvatinib	20mg	QD	PO	Lead in as single agent day 1-7, then to continue daily on Q3 week schedule	Experimental
Pembrolizumab	200 mg	Q3W	IV infusion	Day 1 of each 3 week cycle, starting following 7 day lead in with lenvatinib (Day 8 of study)	Experimental

Trial treatment should begin on the day of randomization or as close as possible to the date on which treatment is allocated/assigned.

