7.1.2 Clinical Procedures and Assessments

7.1.2.1 Adverse Event (AE) Monitoring

The investigator or qualified designee will assess each subject to evaluate for potential new or worsening AEs as specified in the Trial Flow Chart and more frequently if clinically indicated. Adverse experiences will be graded and recorded throughout the study and during the follow-up period according to NCI CTCAE Version 4.03 (see Section 11.2). Toxicities will be characterized in terms regarding seriousness, causality, toxicity grading, and action taken with regard to trial treatment.

Please refer to section 7.2 for detailed information regarding the assessment and recording of AEs.

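### Table 13 has no relationship or action-taken item for lenvatinib and defines seriousness by the Merck product alone, in conflict with 7.1.2.1 and 7.2.2

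*Combined protocol and SAP*

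**What the plan says.** Section 7.2.5 requires a qualified physician to assess all AEs on the items of Table 13. The drug-specific items are these:

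- Seriousness: "A serious adverse event is any adverse event occurring at any dose or during any use of Merck product that" meets one of the listed outcomes.
- Action taken: "Did the adverse event cause Merck product to be discontinued".
- Causality: "Did Merck product cause the adverse event".
- Answers: Yes or No. The negative answer reads "No, there is not a reasonable possibility of Merck product relationship". Its guidance starts "Subject did not receive the Merck product OR temporal sequence of the AE onset relative to administration of Merck product is not reasonable" and adds, as a further ground, that some other cause is the likelier explanation.

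Under Section 9.1, Merck supplies pembrolizumab and Eisai supplies lenvatinib. Table 13 does not name lenvatinib.

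Elsewhere the protocol is wider. Section 7.1.2.1 says "Toxicities will be characterized in terms regarding seriousness, causality, toxicity grading, and action taken with regard to trial treatment". Section 7.2.2 defines a serious adverse event (SAE) by use of study drug(s), sends the reader to Table 13 for detail on the criteria, and requires SAEs judged related to either agent to be reported to the sponsor, Merck and Eisai. Table 6 in Section 5.3 gives lenvatinib as "Lead in as single agent day 1-7, then to continue daily on Q3 week schedule"; pembrolizumab starts on study Day 8.

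**The concern.** This is a two-drug trial with toxicity among its secondary objectives (3.2). Its dose rules are written by agent (Table 7 for pembrolizumab, Table 8 for lenvatinib), and 5.3.1.2 keeps one drug going when the other is held or stopped for toxicity. To interpret an AE, one therefore needs to know which drug the investigator held responsible and which drug was changed. A table that asks about one drug cannot supply that. Attribution by agent is also hard to reconstruct reliably afterwards, so a gap at the time of recording tends to stay a gap.

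**Working it through.** The plan states no figure on this point, so there is nothing to reproduce. The check is a comparison of texts, followed by simple proportions for scale.

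**1. Texts side by side**

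| Item | Table 13 (7.2.5) | Elsewhere |
|---|---|---|
| Seriousness | use of Merck product | use of study drug(s) (7.2.2) |
| Causality | Merck product, Yes or No | causality of every toxicity (7.1.2.1); either agent, for SAEs (7.2.2) |
| Action taken | Merck product stopped or not | action on trial treatment (7.1.2.1) |
| Dechallenge | Merck product stopped or reduced | one agent may be held while the other continues (5.3.1.2) |

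The only way lenvatinib can enter the causality assessment is as a competing explanation, under the component that asks "Is the AE not reasonably explained by another etiology such as underlying disease, other drug(s)/vaccine(s), or other host or environmental factors".

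**2. Lead-in.** Days 1-7 are lenvatinib alone and the first pembrolizumab dose is on Day 8. An AE with onset in that week has no prior pembrolizumab exposure, so it meets the first ground for No. Table 13 then offers nowhere to say whether lenvatinib caused it, what was done with lenvatinib, or whether it resolved when lenvatinib was held. Read literally, an event that meets a seriousness criterion in that week is an SAE under 7.2.2 but falls outside the Table 13 definition.

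**3. After Day 8.** Suppose lenvatinib is held, pembrolizumab continues as 5.3.1.2 directs, and the AE resolves. The dechallenge item asks only about the Merck product, so this informative sequence is not recorded there.

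**4. Late SAEs.** Under the safety measures in 8.1, a subject who stopped treatment without progression has, beyond 30 days from the last dose, only those SAEs captured that are related to study drug or study procedure. Capture then turns on a relatedness judgment, and Table 13 structures that judgment for pembrolizumab only.

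**5. Scale, by assumption.** The documents give no AE-driven action rates for this regimen in this population. Applying background rates to the planned 29 subjects:

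- Lenvatinib discontinuation at 18% (4.1.4.6): 0.18 × 29 = 5.2, about 5. At the 14.2% seen in the phase III thyroid trial (4.1.4.7.3): 0.142 × 29 = 4.1, about 4.
- Lenvatinib dose reduction at 68% (4.1.4.6): 0.68 × 29 = 19.7, about 20. As a low end, 4.2.2.2 describes 10 patients on the combination at 20 mg, of whom one is stated to be on a reduced dose and seven needed no reduction. That is between 1 and 3 of 10: 0.1 × 29 = 2.9 and 0.3 × 29 = 8.7, on short follow-up.

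The range is therefore about 4 to 5 discontinuations and about 3 to 20 dose reductions. Table 13 would record none of them as a lenvatinib action.

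**The case against.** The best reply is that this is leftover template wording with little consequence, and much of that reply stands.

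- A reader might infer that lenvatinib toxicities are coded as unrelated by rule. The documents do not support this. The negative answer denies a relationship to the Merck product only, and for a lead-in AE that is true. The criteria are offered as guidance, with clinical judgment deciding. After Day 8, fatigue, diarrhea, nausea and decreased appetite are common to both drugs (4.1.2.6, 4.1.4.6) and can be answered Yes.
- A reader might infer that reported toxicity will be understated. Section 8.1 summarises toxicity by frequency and grade with no causality filter, and anyone with at least one dose of either drug is evaluable. The secondary toxicity result is not biased.
- A reader might infer that expedited reporting fails. Section 7.2.2 requires attribution of SAEs to either agent, and its minimum narrative covers association with study treatment and whether treatment was stopped.
- A reader might infer that lenvatinib changes go unrecorded altogether. Pill diaries are reviewed at each cycle and treatment records are source documents (10.6.1).
- A reader might set 68% for lenvatinib beside 11.9% for pembrolizumab. The first is dose reductions and the second is discontinuations. Like for like, the figures are 18% and 11.9%.

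The eCRF is also not among the documents and may already hold lenvatinib fields.

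What this reply leaves open is the non-serious AE. Section 7.1.2.1 asks for causality and action on trial treatment, but no item in Table 13 collects them for lenvatinib. Diaries and treatment records show that a dose changed without tying the change to an event.

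**Conclusion.** The concern holds as a gap in safety recording: lenvatinib attribution and action are missing from Table 13, which is different from being recorded falsely. The gap is certain for the lead-in week and likely to matter afterwards whenever lenvatinib alone is changed. It puts three things at risk: per-agent attribution of non-serious AEs, the link between an AE and a lenvatinib hold, reduction or stop, and consistent use of the late SAE rule in 8.1. The seriousness definitions in 7.2.5 and 7.2.2 also contradict each other. No planned primary or secondary result changes.

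The counts above rest on rates from other settings. The section giving 68% and 18% does not state the dose, so they show order of size only. The conclusion also assumes that Table 13 is followed as written; if the eCRF already has lenvatinib fields, what remains is a protocol text to be brought into line. The point should be corrected, because the fix is cheap and the information is hard to recover later.

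**What to change.** In Table 13:

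1. Record relationship separately for pembrolizumab and for lenvatinib, with the exposure, time course, dechallenge and rechallenge prompts applied to each.
2. Record action taken separately for each agent as none, held, reduced or discontinued, as applicable.
3. Define seriousness by use of study drug(s), to match 7.2.2.

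Then confirm that the eCRF carries the same fields, and state in 8.1 that relatedness for late SAE capture means related to either agent or to a study procedure. If subjects have already been enrolled, complete the lenvatinib fields from source notes and flag them as retrospective.

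The cost is a wording change to one table, a clarifying phrase in 8.1, and a few extra fields per AE. Sample size, visits and the planned toxicity summary are unaffected.

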7.2.6 Responsibility for Reporting Adverse Events

All Adverse Events will be reported to regulatory authorities, IRB/IECs and investigators in accordance with all applicable global laws and regulations.

The Principal Investigator is responsible for reporting all unexpected problems involving risk to participants or others to NYU Perlmutter Cancer Center CTO.

7.2.7 Stopping Rules

As no adverse events are anticipated given the low level of risk in this trial, there are no formalized stopping rules. However, should any serious and unexpected adverse events occur, the principal investigator will consider whether early stopping is appropriate.

7.2.8 Medical Monitoring Plan

It is the responsibility of the Principal Investigator to oversee the safety of the study at his/her site. This safety monitoring will include careful assessment and appropriate reporting of adverse events as noted above, as well as the construction and implementation of a site data and safety-monitoring plan. The Data Safety and Monitoring Committee (DSMC) will review the study at least annually. Medical monitoring will include a regular assessment of the number and type of serious adverse events.

7.2.8.1 Data and Safety Monitoring Plan

Per the NYU PCC Institutional Data Safety and Monitoring Plan, this phase II trial will be monitored by DSMC at least annually (from the date the first subject is enrolled), at dose escalation point and subsequent cohort activation, and at the completion of the study prior to study closure. This review includes accrual data, subject demographics and adverse events. Principal Investigators are required to attend the review of their studies. Additional reviews can be scheduled based on SAE reports, investigator identified issues, external information, etc.

